## LIST OF ABBREVIATIONS

ABO	Blood types A, B, and O
AE	Adverse event
ALT	Alanine aminotransferase
aPTT	Activated partial thromboplastin time
AST	Aspartate aminotransferase
ATC	Anatomical-Therapeutic-Chemical
BP	Blood pressure
BUN	Blood urea nitrogen
CBC	Complete blood count
CSP	Clinical study protocol
CTCAE	Common Terminology Criteria for Adverse Events
DMC	Data Monitoring Committee
ETP	Endogenous thrombin potential
EKG	Electrocardiogram
GGT	Gamma glutamyl transferase
hs	High sensitivity
INR	International normalized ratio
LDH	Lactate dehydrogenase
MPV	Mean platelet volume
NCI	National Cancer Institute
PF	Prothrombin fragment
PI	Principal Investigator
PT	Preferred term or prothrombin time (context dependent)
RBC	Red blood cell
Rh	Rhesus
ROTEM	Rotational thromboelastometry
SAE	Serious adverse event
TAT	Thrombin antithrombin
TEAE	Treatment-emergent adverse event
TEG	Thromboelastography
TGA	Thrombin generation assay
TGPU	Thrombin generation potency units
WBC	White blood cell
WHO	World Health Organization

## 1 INTRODUCTION

This document outlines the methods of statistical analysis and data presentation associated with clinical study protocol (CSP) 2017-1, describing a Phase 1, multicenter, open-label, dose-escalation study. Within this study, the effects of escalating infusion doses of the investigational product, Thrombosomes®, will be assessed within a target population of actively-bleeding, thrombocytopenic patients (with platelet counts 5,000-70,000/ $\mu$ L). Patient inclusion will further be restricted to those with modified World Health Organization (WHO) bleeding severity scores of grade 1 (including only those patients with epistaxis, hematuria, oral petechiae, oropharyngeal bleeding, or bleeding at invasive or other wound sites) or grade 2, with bleeding due to hematologic/oncologic disease or bone marrow aplasia secondary to chemotherapy or radiotherapy. While the overall study design, study objectives and endpoints, and proposed methods for manipulating, analyzing, and presenting data are described below, the reader is referred to the CSP and case report forms for detailed descriptions of the investigational product, full list of patient inclusion/exclusion criteria, and data collection methods.

## 2 STUDY OBJECTIVES AND ENDPOINTS

### 2.1 Study Objectives

#### 2.1.1 Primary Objective

The primary objective of this study is to assess the effect of escalating infusion doses of Thrombosomes on the safety of actively-bleeding, thrombocytopenic patients.

Three dose levels, including 5 mL ( $9.45 \times 10^7$  particles/kg or 165 thrombin generation potency units [TGPU] per kg), 10 mL ( $1.89 \times 10^8$  particles/kg or 330 TGPU/kg), and 20 mL ( $3.78 \times 10^8$  particles/kg or 660 TGPU/kg), will be studied across 3 sequentially enrolled patient cohorts. Incidence of treatment-emergent adverse events (TEAEs) and serious adverse events (TESAEs), application of suspension or stopping rules, and abnormality or worsening in measures of bleeding severity, coagulation, hematology, serum chemistry, vital signs, and cardiac, physical, and neurologic statuses will be used as indicators of safety.

#### 2.1.2 Secondary Objective

The secondary objective of this study is to assess potential efficacy of Thrombosomes for managing bleeding in actively-bleeding, thrombocytopenic patients.

Efficacy will be assessed within and across 3 sequentially enrolled patient cohorts, treated, respectively, at 3 escalating dose levels (see *Primary Objective* above). Post-infusion patterns showing stability or change toward clinical improvement in hematology measures will be used as preliminary indicators of possible product efficacy in bleeding management, and patterns in the receipt of transfused blood products will also be examined.

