### 1.8.2 Secondary

- Assess the effect, on WHO bleeding score, of increasing doses of allogeneic Thrombosomes.
- Assess the effect of increasing doses of allogeneic Thrombosomes on measures of coagulation.

\* Note: Only a subset of patients with Grade 1 bleeding who have either epistaxis, hematuria, oral petechiae, oropharyngeal bleeding, or bleeding at invasive or other wound sites.

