### 1.9.2.2 Additional Hemostatic Therapy: All Cohorts

This product is not expected to increase the platelet corrected count increment (CCI). The infusion of platelets for six hours prior and one hour after infusion of Thrombosomes is

restricted. However, at any time, if the patient's clinical bleeding remains unchanged or deteriorates with additional or worsening bleeding, the patient's physician(s) may transfuse the patient with blood products, hemostatic agents, or coagulation factors without limitation. The study patient will be followed for safety data for 30 (+2) days post-infusion of the dose of Thrombosomes.

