### **1.9.9 Safety Endpoints**

Primary: The occurrence and frequency of AEs, SAEs, and thromboembolic events as determined by clinical signs and symptoms, physical exam including neurological assessment, and laboratory studies.

Secondary:

- Describe the effect of increasing doses of allogeneic Thrombosomes on bleeding including changes in WHO bleeding grade.
- Describe the effect of increasing doses of allogeneic Thrombosomes on coagulation measures.

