### **1.16 Data Analysis**

Separate data summaries will be prepared for each cohort:

- Demographic and medical history data will be summarized. For quantitative variables, summaries will include the sample size, mean, median, standard deviation, minimum, and maximum. For qualitative variables summaries include the number and percent of patients for each outcome.
- Exploratory analyses will include the observed response and the change from baseline to each of the post-infusion time points for each of the laboratory tests (hematology, coagulation, platelet and chemistry). Additionally, summaries of the number and percent of patients with both a change of  $>5\%$  from baseline and whose results are outside of reference ranges will be displayed. For quantitative variables summaries of the observed response and the change from baseline to each of the post-baseline time points will include the sample size, mean, median, standard deviation, minimum, and maximum. Additionally, for the change from baseline summaries, the statistical significance will be determined using either a t-test or the Wilcoxon Signed Rank test, as appropriate. Summaries for qualitative variables will include the number and percent of patients for each outcome.
- Incidence of AEs and SAEs per patient and by body system will be summarized showing the number and percent of patients for each outcome. Summaries will also be prepared by severity and relationship to treatment.
- Summaries of vital signs and clinical data including WHO bleeding scores will include the observed response and the change from baseline to each of the post-infusion time points for each of the variables. For quantitative variables summaries of the observed response and the change from baseline to each of the post-baseline time points will include the sample size, mean, median, standard deviation, minimum, and maximum. Additionally, for the change from baseline summaries, the statistical significance will be determined using either a t-test or the Wilcoxon Signed Rank test, as appropriate. Summaries for qualitative variables will include the number and percent of patients for each outcome.

A statistical analysis plan will be developed as part of the data analysis plan.

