Secondary Safety Endpoints : “Describe the effect of increasing doses of allogeneic Thrombosomes on bleeding including changes in WHO bleeding grade” and “Describe the effect of increasing doses of allogeneic Thrombosomes on coagulation measures”.	Section 1.9.9, Page 18	Rephrased to explicitly define endpoints and focus on quantification of post-infusion patterns in hematology measures and receipt of transfused blood products.	Section 2.2.2, Page 7
Patient Numbers : “... Approximate number of patients enrolled: 30... Maximum Number of Patients Completed: 24...”, without explicit definition of “enrolled” or “completed”.	Section 1.10.1, Pages 18-19	Added text to the description of overall study design in order to explicitly define “enrolled” and “completed”.	Section 3.1, Page 9
Sample Size Justification : “... there is no statistical basis for the selection of the sample size. The sample size, 8 patients per cohort, was selected to provide a reasonable balance in order to assess safety while minimizing the number of patients potentially at risk.”	Section 1.13, Page 21	Rephrased with same general meaning but added detail and description of the employed rule-of-thumb for limiting the sample size at individual study sites.	Section 4, Page 14

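### The SAP's secondary efficacy readout replaces WHO bleeding and coagulation with hematology and transfusion use, and its hematology categories are confounded by transfusion

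*SAP*

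**What the plan says.** **Protocol.** Section 1.8.2 has two secondary objectives. The first is "Assess the effect, on WHO bleeding score, of increasing doses of allogeneic Thrombosomes"; the second asks the same question of coagulation. Section 1.9.9 repeats them as secondary endpoints, the first being "Describe the effect of increasing doses of allogeneic Thrombosomes on bleeding including changes in WHO bleeding grade". Hematology appears in neither section. It enters in 1.16, which says "Exploratory analyses will include the observed response and the change from baseline to each of the post-infusion time points for each of the laboratory tests".

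**SAP.** The secondary objective (2.1.2) is efficacy in managing bleeding, and its indicators are: "Post-infusion patterns showing stability or change toward clinical improvement in hematology measures will be used as preliminary indicators of possible product efficacy", plus transfusion. The secondary endpoints in 2.2.2 are hematology stability or improvement, patients transfused, and units transfused. Section 9 analyses only hemoglobin, hematocrit, platelets and transfusions. WHO bleeding and coagulation are listed as primary endpoints in 2.2.1 and analysed as safety in 8.2 and 8.3. Section 11 records that the secondary endpoints were reworded to "focus on quantification of post-infusion patterns in hematology measures and receipt of transfused blood products". It gives no reason specific to this change.

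**Transfusion.** Protocol 1.9.2.2 restricts platelets from 6 hours before to 1 hour after infusion. Otherwise it sets no limit on blood products when bleeding is unchanged or worse. The same section says "This product is not expected to increase the platelet corrected count increment (CCI").

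**The concern.** The stated question is whether the product helps to manage bleeding, yet the section of the SAP that answers it contains no measure of bleeding. What it does contain, a rise in hemoglobin, hematocrit or platelets, is what a transfusion is given to produce, and transfusion is most likely when bleeding has not responded. The efficacy table could therefore look favourable because patients were rescued.

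Protocol 1.9.1 says that the data will inform the design of later trials in bleeding patients. A misleading table could carry over into the choice of endpoint or dose there.

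**Working it through.** **1. Endpoints side by side**

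| Measure | Protocol 1.8.2, 1.9.9 and 1.16 | SAP |
|---|---|---|
| WHO bleeding grade | Secondary | Primary, safety (2.2.1, 8.2) |
| Coagulation | Secondary; laboratory change called exploratory in 1.16 | Primary, safety (2.2.1, 8.3) |
| Hematology change | Exploratory (1.16) | Secondary, efficacy (2.2.2, 9.1) |
| Transfusion use | Recorded; not an endpoint | Secondary, efficacy (2.2.2, 9.2) |

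**2. The 9.1 rule applied to one patient**

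Inputs from SAP 9.1: improvement is +1 g/dL hemoglobin, +3% hematocrit or +5,000/µL platelets; worsening is the mirror image; all values in the timeframe count; a patient who shows both is classed as improved.

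Suppose bleeding worsens and platelets are 5,000/µL below baseline at 6 hours. Platelets are then transfused, and the 24-hour count is 5,000/µL above baseline. Both conditions are met, so the patient is recorded as improved, both through 24 hours and through Day 6.

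Three features of the plan make this likely to matter:

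- A CBC is required within 1 hour (+30 minutes) after any transfusion on Days 1–6 (footnote 6 of both schedules). SAP 6.2 may treat some of these as unscheduled. On Days 3–5, however, the window is the whole day, so they fall inside it.
- The transfusion subgroups in SAP 6.6 cover platelets only to 1 hour after infusion and other products only to 24 hours. A patient given platelets at 2 hours is in the no-platelets subgroup unless platelets were also given inside the window.
- Those subgroups are counted in a population table and used in laboratory plots (8.3), not in 9.1. SAP 6.5 plans no stratified or adjusted analysis.

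**3. Possible size of the transfusion effect**

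Let *t* be the share of patients whose transfusion lifts a value past the threshold (assumed), and *p* the share who would reach it anyway. The expected share improved with no product effect is *t* + (1 − *t*)*p*. Expected number out of 8 per cohort:

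| *t* | *p* = 0 | *p* = 0.25 |
|---|---|---|
| 0.25 | 2.0 | 3.5 |
| 0.50 | 4.0 | 5.0 |
| 0.75 | 6.0 | 6.5 |

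**4. Random variation alone**

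This is a simulation of 400,000 patients with no product effect and no transfusion. Values are independent and normal around the patient's own mean, with one shared baseline. The within-patient SD is assumed, as a fraction of the threshold. Three post-infusion values represent the 24-hour timeframe (1, 6 and 24 hours); seven represent Day 6 in a hospitalized patient (adding Days 3, 4, 5 and 6).

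| SD / threshold | Improved, 3 values | Improved, 7 values | Stable or improved, 3 values | Stable or improved, 7 values |
|---|---|---|---|---|
| 0.25 | 1% | 1% | 99% | 99% |
| 0.50 | 18% | 29% | 83% | 72% |
| 0.75 | 35% | 50% | 68% | 61% |
| 1.00 | 45% | 62% | 63% | 64% |

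The override favours improvement even though the simulated variation is symmetric. At SD = 1.00 with seven values, 61.5% are classed as improved and 35.7% as worsened; the gap of 25.8 points is the 25.8% who met both conditions.

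**5. The test of WHO change**

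Protocol 1.16 says "Summaries of vital signs and clinical data including WHO bleeding scores will include the observed response and the change from baseline", then provides a t-test or Wilcoxon signed-rank test for change-from-baseline summaries. SAP 8.2 has only a between-cohort Fisher's exact test of grade 2 or higher at each time-point. That test does not use the patient's own baseline and cannot register a grade 1 bleed resolving to grade 0. Section 11 does not mention the difference.

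**The case against.** Much can be said for the SAP, and it rules out several stronger readings.

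- **A reader might infer that the bleeding and coagulation results are lost.** They are not. Both are primary endpoints, WHO grade change is tabulated by cohort and time-point including decreases of one and two grades, and coagulation keeps its Wilcoxon tests. The protocol itself places both under a safety-endpoints heading.
- **A reader might infer that doses are never compared on bleeding.** The Fisher test in 8.2 compares cohorts. A paired within-cohort test would not compare doses.
- **A reader might infer that efficacy rests on measures the product is not expected to move.** The protocol's statement covers only the platelet corrected count increment, which is not the raw count. Hemoglobin, hematocrit and transfusion use could respond to less bleeding.
- **A reader might infer that a planned test was certainly removed.** In 1.16 the test follows a sentence on quantitative variables, while qualitative ones get counts and percentages. WHO grade is ordinal, so either reading is possible.
- **A reader might infer a formal efficacy claim.** The SAP calls these measures preliminary, attaches no test to the 9.1 categories, and does not derive 8 per cohort statistically.

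SAP 9.2 also reports transfusions by visit, product and reason, so some of the confounding will be visible. Moreover, transfusion can lower WHO grade too, so restoring WHO change does not by itself remove confounding.

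All of this stands. It does not answer the 9.1 rule, which allows a rescued patient to appear as improved and leaves the reader to work that out from other tables.

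**Conclusion.** The concern holds in a limited form. The secondary endpoints were reclassified, with disclosure but no specific reason, and the efficacy section has no bleeding measure. The 9.1 categories cannot separate a product effect from transfusion, and the platelet component also sits poorly with the protocol's own statement on the count increment.

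The size cannot be fixed from the documents, which give neither a transfusion rate nor a within-patient SD. Under the assumptions shown, transfusion alone gives an expected 2 to 6 of 8 improved per cohort, and random variation alone puts 61% to 99% of patients in the stable-or-improved group that forms the first SAP secondary endpoint. The simulation assumes independent errors and no time trend. It shows how the rule behaves and does not predict this trial's results.

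The safety evaluation is unaffected. The documents do not support saying that bleeding data go unreported or that a formal efficacy conclusion is at risk. What is at risk is how a descriptive efficacy table will be read.

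**What to change.** 1. In SAP 2.1.2, 2.2.2 and Section 9, restore change in WHO bleeding grade and coagulation measures as the secondary endpoints. The tables are already planned (14.3.3 and 14.3.4). Label hematology patterns and transfusion summaries exploratory.
2. In 9.1, classify hemoglobin, hematocrit and platelets only from values before the first post-infusion transfusion, with a row for patients who have no such value. Alternatively, show the categories separately for transfused and non-transfused patients. This needs a flag covering the whole timeframe, because the 6.6 subgroups do not.
3. Either add the paired signed-rank test of WHO change as a descriptive result, or list its omission in Section 11.

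**Cost.** SAP wording, one derived flag or cut-off, and possibly one column of P-values. Hematology loses its efficacy label and fewer values enter the 9.1 categories. Transfusion is itself a post-infusion outcome, so either version of step 2 remains descriptive. Paired P-values would be uncontrolled, unadjusted for multiplicity, and exposed both to transfusion effects and to regression to the mean, since patients enter because they are bleeding. They should be reported as descriptive only.

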### 2.2.2 Secondary Endpoints

Multiple secondary endpoints will be quantified per patient cohort (i.e., by dose level), as well as overall (i.e., across all 3 dose levels):

- Number and percentage of patients who, from baseline to post-baseline time-points, show either stability (i.e., no change) or an intermittent or sustained change toward clinical improvement in hematology measures, with or without reaching normal levels.
- Number and percentage of patients who receive transfused blood products following infusion.
- Statistics describing central tendency and variability in the numbers of units of blood products transfused following infusion.

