## 9.1 Clinical Laboratory Assessments

Laboratory assessments to be used in efficacy analyses will include select hematology measures (hemoglobin, hematocrit, and platelets). Within a single table for each of 2 populations (Safety and Evaluable), the numbers and percentages of patients will be presented by categorized patterns of post-infusion change, including clinical improvement, stability/no change, and clinical worsening, for each of 2 post-infusion timeframes (infusion through the 24-hour post-infusion visit and infusion through the Day-6 visit). For each patient, categorization will require consideration of all measurements recorded across all time-points within the timeframe. For each hematology measure, clinical improvement and worsening will be defined as shown below. The category of stability/no change will apply by default when, for an individual patient, neither improved nor worsened conditions have been observed following infusion. When both improved conditions and worsened conditions have been distinctly observed at different time-points, the patient will fall into the category of clinical improvement.

Clinical improvement will be defined by:

- Hemoglobin increase of 1 g/dL
- Hematocrit increase of 3%
- Platelet count increase of 5,000/ $\mu$ L

Clinical worsening will be defined by:

- Hemoglobin decrease of 1 g/dL
- Hematocrit decrease of 3%
- Platelet count decrease of 5,000/ $\mu$ L

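### The hematology efficacy endpoint counts no change as favourable and resolves mixed patterns as improvement, so its pooled percentage has no interpretable value under no effect

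*SAP*

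**What the plan says.** The secondary objective (SAP 2.1.2) treats both stability and improvement as signals: "Post-infusion patterns showing stability or change toward clinical improvement in hematology measures will be used as preliminary indicators of possible product efficacy" in bleeding management. SAP 2.2.2 turns this into a single count, the number and percentage of patients who "show either stability (i.e., no change) or an intermittent or sustained change toward clinical improvement in hematology measures, with or without reaching normal levels".

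SAP 9.1 applies the idea to hemoglobin, hematocrit and platelets. The thresholds mirror each other: a rise or a fall of 1 g/dL, 3% or 5,000/µL. All counts in the timeframe are considered. Two rules settle the classification:

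- Default: "The category of stability/no change will apply by default when, for an individual patient, neither improved nor worsened conditions have been observed following infusion".
- Mixed pattern: "When both improved conditions and worsened conditions have been distinctly observed at different time-points, the patient will fall into the category of clinical improvement".

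SAP 9.1 tabulates "categorized patterns of post-infusion change, including clinical improvement, stability/no change, and clinical worsening, for each of 2 post-infusion timeframes" (through 24 hours and through Day 6). It names no test, success threshold or reference rate for this endpoint. Every enrolled patient receives the product, in three dose cohorts of 8 (Protocol 1.9.2; SAP 3.1). For platelets, Protocol 1.9.2.2 says: "This product is not expected to increase the platelet corrected count increment (CCI").

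**The concern.** Put the two SAP 9.1 rules together with the pooled count in 2.2.2. A patient is favourable unless a threshold fall was seen and no threshold rise was seen. A patient in whom nothing happens is a success, and so is one whose counts cross both thresholds. No change is what an inert infusion would produce in a patient with steady counts.

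Without a concurrent control or a stated background rate, a result such as 7 of 8 stable or improved cannot be attributed to the product. Protocol 1.9.1 says that the data are meant to support the design of later protocols in bleeding patients, so a flattering percentage could carry weight there. The problem exists even with complete data and no transfusions. It is separate from how missing or post-transfusion counts are handled.

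**Working it through.** The plan states no expected rate, SD or power for this endpoint, so there is no figure of its own to reproduce.

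**Inputs from the documents.** The thresholds and the two classification rules come from SAP 9.1. The schedule (Protocol Table 4, SAP Table 2) gives 3 post-infusion counts through 24 hours (1, 6 and 24 h), 4 with Day 6, and 7 if the patient is hospitalized on Days 3–5.

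**Assumptions (not in the documents).** Baseline and each later count vary independently and normally around the patient's level, with SD 0.3 to 1.0 threshold. That is 0.3–1.0 g/dL for hemoglobin and 1,500–5,000/µL for platelets. Data are complete, no one is transfused, and the product does nothing. Any decline is spread in equal steps over the counts and reaches the stated size at the last one. A threshold counts as crossed when the change is at least that large.

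**Analytic check, no drift.** With mirror-image thresholds and symmetric changes, P(improved only) = P(worsened only). Hence P(favourable) = 0.5 + 0.5 × [P(stable) + P(mixed)]. This is at least 50%, but only under that symmetry.

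**Simulation of the SAP 9.1 rule.** Percent stable or improved for an inert product (each range spans 3 and 4 counts):

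| SD (thresholds) | No drift | Half-threshold decline | Full-threshold decline |
|---|---|---|---|
| 0.3 | 97–98 | 82–84 | 42–45 |
| 0.5 | 79–83 | 60–64 | 36–40 |
| 0.75 | 65–68 | 51–54 | 37–39 |
| 1.0 | 62–63 | 51–52 | 41 |

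At SD 0.3 with no drift, 94–95% of patients are simply stable. With 7 counts, SD 0.75 and a half-threshold decline, the rate is 48%. The shape of the decline matters too. If it follows clock time instead of equal steps, the last two columns become about 56–87% and 47–52%.

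**Effect of the mixed-pattern rule, no drift.**

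- 4 counts, SD 1.0: stable 11%, mixed 12%, improved only 38%, worsened only 38%. Identity check: 0.5 + 0.5 × (0.11 + 0.12) ≈ 0.62, as in the table. The rule turns 38 against 38 into about 51% improved against 38% worsened.
- 7 counts, SD 0.75: about 50% against 39%.
- SD 0.3: almost no one is mixed, and the rule does nothing.

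**What 8 patients can show.** If the inert rate were 65%, 80% or 97%, the chance of at least 6 of 8 favourable would be 0.43, 0.80 or 0.999. Even 8 of 8 has an exact 95% interval of 63–100%, which contains two of these rates fully above its lower limit of 63% and the third, 65%, just above it.

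**The case against.** Several counter-arguments have weight.

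- **The categories are already separate.** SAP 9.1 and Tables 14.2.1.1 and 14.2.1.2 show improvement, stability and worsening by cohort, and no pooled row is specified. This is true, and it limits the harm. But the endpoint declared in 2.2.2 is still the pooled count, 2.1.2 still calls stability an indicator of efficacy, and the improvement row still absorbs mixed patients.
- **It is descriptive Phase 1 work.** The SAP speaks of preliminary indicators, assessed within and across doses, with no decision rule. This stands. The plan does not commit anyone to declaring efficacy, and a reader should not infer that it does.
- **Lack of a control arm is a design feature.** This also stands. The point is not that the trial needs a control, but that this endpoint has no meaning as an efficacy percentage without one.
- **A hemoglobin that stops falling is what a hemostat should produce.** This is reasonable clinically, but a single-arm count cannot tell that patient from one who was never going to fall. The sentence on corrected count increment concerns platelets only and says nothing about hemoglobin or hematocrit.

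A reader might also infer that an inert product must score at least 50%, or that some narrow range is typical. The documents support neither. The 50% bound needs symmetric changes with no downward drift, which cannot be assumed in bleeding patients with leukemia or marrow aplasia. Any range depends on SDs that the documents do not give.

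**Conclusion.** The concern holds for the wording of the endpoint and for the mixed-pattern rule. The pooled percentage has no interpretable value under no effect: about 62–98%, 51–84% or 36–45% for an inert product with no, half-threshold or full-threshold decline. These figures rest on the assumed SDs of 0.3–1.0 threshold, 3 or 4 complete counts, no transfusion and equal-step decline. They show how widely the benchmark moves and do not estimate it. The mixed-pattern rule adds a one-sided tilt toward improvement when counts are noisy or numerous, and is negligible when they are not. The safety objectives are untouched, and the separate rows in SAP 9.1 already give part of the remedy. The change is worth making because it is specific, nearly free and removes a favourable bias.

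**What to change.** - **SAP 2.2.2:** replace the pooled count of stable or improved patients with separate counts for each measure, timeframe and cohort.
- **SAP 9.1 and Tables 14.2.1.1 and 14.2.1.2:** report four mutually exclusive rows: improved only, worsened only, mixed (both a threshold rise and a threshold fall seen) and stable. Delete the rule that sends mixed patients to improvement.
- **SAP 2.1.2:** state that, without a control, a stable count alone is not evidence of efficacy.
- **Reporting:** keep it descriptive. Do not add a sign test of improved against worsened with a 50:50 reference, because that reference assumes no drift and no transfusion effect. In the same simulation (3–4 counts, SD 0.3–1.0), an inert product with a half-threshold decline gives an improved share of only 2–37% among improved-only plus worsened-only patients. A half-threshold rise gives the mirror image, 63–98%.

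The cost is SAP wording and one added row in two tables, with no new data. The downside for the sponsor is that the headline favourable percentage becomes smaller.
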